#### **9.2.3. Complaint Handling**

Lilly collects product complaints on IPs and drug delivery systems used in clinical trials in order to ensure the safety of study participants, monitor quality, and to facilitate process and product improvements.

Subjects should be instructed to contact the investigator as soon as possible if he or she has a complaint or problem with the IP so that the situation can be assessed.

### **9.3. Treatment of Overdose**

For the purposes of this study, an overdose of tirzepatide is considered any dose higher than the dose assigned through randomization or as defined by protocol. There is no specific antidote. The subject should be watched for GI symptoms and hypoglycemia. Treatment is supportive, depending on the subject’s symptoms. For detailed information, refer to the IB for tirzepatide.

## 9.4. Safety

### 9.4.1. Laboratory Tests

For each subject, laboratory tests to assess PD and safety of study treatment will be performed throughout the study according to Section 2 (Schedule of Activities). A detailed list of laboratory analytes is provided in [Appendix 2](#). Any clinically significant findings from laboratory tests that result in a diagnosis and that occur after the subject receives the first dose of the IP should be reported to Lilly, or its designee, as an AE via eCRF.

### 9.4.2. Vital Signs

Vital sign measurements should be taken before obtaining an ECG tracing, at visits where required (see Section 2, Schedule of Activities), and before collection of blood samples for laboratory testing. For each parameter, 2 measurements will be taken using the same arm. An appropriately sized cuff (cuff bladder encircling at least 80% of the arm) should be used to ensure the accuracy of blood pressure measurements. The arm used for the blood pressure measurement should be supported at heart level. Each measurement of sitting heart rate and blood pressure is to be recorded in the eCRF. Any AE related to changes in blood pressure and heart rate should be reported, per requirements provided in Section 9.2.

### 9.4.3. Electrocardiograms

For each subject, a single 12-lead digital ECG for safety will be collected according to Section 2 (Schedule of Activities).

Electrocardiograms must be recorded before collecting any blood samples. Subjects must be supine for approximately 5 to 10 minutes before ECG collection and remain supine but awake during ECG collection. Electrocardiograms may be obtained at additional times, when deemed clinically necessary. All ECGs recorded should be stored at the investigational site.

Electrocardiograms will be interpreted by a qualified physician (the investigator or qualified designee) at the site as soon after the time of ECG collection as possible, and ideally while the subject is still present, to determine whether the subject meets entry criteria at the relevant visit(s) and for immediate subject management, should any clinically relevant findings be identified.

If a clinically significant finding is identified (including, but not limited to, changes in QT/QTc interval from baseline) after enrollment, the investigator will determine if the subject can continue in the study. The investigator, or qualified designee, is responsible for determining if any change in subject management is needed, and must document his/her review of the ECG printed at the time of collection. Any clinically significant findings from ECGs that result in a diagnosis and that occur after the subject receives the first dose of the IP should be reported to Lilly, or its designee, as an AE via eCRF.

#### **9.4.4. Physical Examinations**

Physical examinations and routine medical assessments will be conducted as specified in Section 2 (Schedule of Activities) and as clinically indicated.

#### **9.4.5. Safety Monitoring**

The Lilly CP or CRP/scientist will monitor safety data throughout the course of the study.

Lilly will review SAEs within time frames mandated by company procedures. The Lilly CP or CRP will periodically review the following data:

- trends in safety data
- safety laboratory analytes including glucose, amylase, and lipase
- serious and nonserious AEs, including AEs of interest (GI events, hypoglycemia, injection-site reactions, hypersensitivity reactions) and reported and adjudicated pancreatitis

When appropriate, the Lilly CP or CRP will consult with the functionally independent Global Patient Safety therapeutic area physician or clinical research scientist.

##### **9.4.5.1. Hepatic Safety**

If a study subject experiences elevated ALT  $\geq 3$ X ULN, ALP  $\geq 2$ X ULN, or elevated TBL  $\geq 2$ X ULN, liver tests (Appendix 4) should be repeated within 3 to 5 days including ALT, AST, ALP, TBL, direct bilirubin, gamma-glutamyl transferase, and creatinine kinase to confirm the abnormality and to determine if it is increasing or decreasing. If the abnormality persists or worsens, clinical and laboratory monitoring should be initiated by the investigator based on consultation with the Lilly CP or CRP. Monitoring should continue until levels normalize and/or are returning to approximate baseline levels.

Additional safety data should be collected if 1 or more of the following conditions occur:

- elevation of serum ALT to  $\geq 5$ X ULN on two or more consecutive blood tests
- elevated serum TBL to  $\geq 2$ X ULN (except for cases of known Gilbert's syndrome)
- elevation of serum ALP to  $\geq 2$ X ULN on 2 or more consecutive blood tests
- patient/subject discontinued from treatment due to a hepatic event or abnormality of liver tests
- hepatic event considered to be a SAE

#### **9.5. Pharmacokinetics**

At the visits and times specified in the Schedule of Activities (Section 2), venous blood samples of approximately 3 mL each will be collected to determine the plasma concentrations of tirzepatide. A maximum of 3 samples may be collected at additional time points during the study if warranted and agreed upon between both the investigator and sponsor. Instructions for

the collection and handling of blood samples will be provided by the sponsor. The actual date and 24-hour clock time of each sampling will be recorded.

### **9.5.1. Bioanalysis**

Samples will be analyzed at a laboratory approved by the sponsor and stored at a facility designated by the sponsor.

Concentrations of tirzepatide will be assayed using a validated liquid chromatography mass spectrometry method. Analyses of samples collected from placebo-treated subjects are not planned.

Bioanalytical samples collected to measure IP concentrations will be retained for a maximum of 2 years following last subject visit for the study. During this time, samples remaining after the bioanalyses may be used for exploratory analyses such as metabolism, protein binding work, and/or bioanalytical method cross-validation.

## **9.6. Pharmacodynamics**

The sample(s) will be stored for up to a maximum of 1 year after the last subject visit for the study at a facility selected by the sponsor.

Briefly, PD assessments will include parameters of energy expenditure, appetite (appetite sensations and desire for specific foods) and food intake, substrate utilization (oxidation), metabolic flexibility, and insulin sensitivity. A detailed description of PD efficacy measures is provided in Section 9.1 (Efficacy Assessments). A description of procedures for obtaining the samples for PD parameters is detailed in [Appendix 6](#).

### **9.6.1. Immunogenicity Assessments**

For immunogenicity testing, venous blood samples of approximately 10 mL will be collected from each subject according to Section 2 (Schedule of Activities) to determine antibody production against tirzepatide. Additional samples may be collected if there is a possibility that an AE is immunologically mediated. All samples for immunogenicity testing should have a time-matched sample for PK analysis where relevant. Detailed instructions on the sample collections will be provided by Lilly or its designee. The actual date and 24-hour clock time of each sampling will be recorded.

Immunogenicity will be assessed by a validated assay designed to detect ADAs in the presence of tirzepatide at a laboratory approved by the sponsor. Antibodies may be further evaluated for their ability to neutralize the activity of the tirzepatide on GIP and GLP-1 receptors. Positive tirzepatide ADA samples may also be tested for cross-reactivity against native GIP and GLP-1, and, if positive, may then be tested for neutralizing antibodies against native GIP and/or GLP-1.

All subjects will have an ADA sample measured at ET and at the safety follow-up visit. A risk-based approach will be used to monitor subjects who develop TE-ADA, defined in Section 10.3.4 (Evaluation of Immunogenicity).

Subjects who have clinically significant TE-ADA at early discontinuation or at the safety follow-up visit, may be asked to return for additional follow-up testing.

A clinically significant TE-ADA will be defined as any TE-ADA with:

- a high titer ( $\geq 1280$ ) or an increasing titer from last measured value, and/or
- an association with a moderate-to-severe injection site reaction or systemic hypersensitivity AE

Every attempt should be made to contact subjects for the follow-up immunogenicity assessment; however, if subjects are unwilling or unable to return for the visit, this is not considered a protocol violation.

Samples will be retained for a maximum of 15 years after the last subject visit, or for a shorter period if local regulations and IRBs allow, at a facility selected by the sponsor. The duration allows the sponsor to respond to future regulatory requests related to tirzepatide. Any samples remaining after 15 years will be destroyed.

### **9.6.2. Body Weight and Waist Circumference**

Weight will be measured according to the schedule provided in Section 2 (Schedule of Activities). Subjects will be weighed at approximately the same time in the morning, before dosing and after an overnight fast and evacuation of the bowel and bladder, if possible. Weight will be measured twice on each scheduled occasion, with the subject stepping off the scale between measurements. A third measurement will be made if the first 2 measurements are  $>0.5$  kg apart. The 2 closest measurements will be recorded. Wherever possible, the same scale will be used for all weight measurements throughout the study, and the scale will not be moved or recalibrated. Weight measurements will be recorded in the source document and the eCRF.

Waist circumference will be measured at the midpoint between the inferior border of the rib cage and the superior aspect of the iliac crest. The subject will stand in a straight, upright position with feet together and arms at the side. The area measured will be cleared of all clothing other than undergarments. The measurement should be taken at the end of normal expiration. Two separate measures will be taken and steps are repeated until 2 measurements are obtained within 0.5 cm of each other.

## **9.7. Genetics**

A blood sample will be collected for pharmacogenetic analysis as specified in the Schedule of Activities, where local regulations allow.

Samples will not be used to conduct unspecified disease or population genetic research either now or in the future. Samples will be used to investigate variable exposure or response to tirzepatide and to investigate genetic variants thought to play a role in type 2 diabetes, obesity, and/or diabetic complications. Assessment of variable response may include evaluation of AEs or differences in efficacy.

All samples will be coded with the subject number. These samples and any data generated can be linked back to the subject only by the investigative site personnel.

Samples will be retained for a maximum of 15 years after the last subject visit, or for a shorter period if local regulations and/or IRBs impose shorter time limits, for the study at a facility selected by Lilly. This retention period enables use of new technologies, response to regulatory questions, and investigation of variable response that may not be observed until later in the development of tirzepatide or after tirzepatide is commercially available.

Molecular technologies are expected to improve during the 15 year storage period and therefore cannot be specifically named. However, existing approaches include whole genome or exome sequencing, genome wide association studies, multiplex assays, and candidate gene studies. Regardless of technology utilized, data generated will be used only for the specific research scope described in this section.

## **9.8. Biomarkers**

Biomarker research is performed to address questions of relevance to drug disposition, target engagement, PD, mechanism of action, variability of subject response (including safety), and clinical outcome. Sample collection is incorporated into clinical studies to enable examination of these questions through measurement of biomolecules including DNA, RNA, proteins, lipids, and other cellular elements.

Serum and plasma samples for non-pharmacogenetic biomarker research will be collected at the times specified in the Schedule of Activities (Section 2) where local regulations allow.

Samples will be used for research on the drug target, disease process, variable response to tirzepatide, pathways associated with T2DM, obesity, and/or diabetic complications, mechanism of action of tirzepatide, and/or research method, or for validating diagnostic tools or assay(s) related to type 2 diabetes, obesity, or diabetic complications.

All samples will be coded with the subject number. These samples and any data generated can be linked back to the subject only by the investigative site personnel.

Samples will be retained for a maximum of 15 years after the last subject visit, or for a shorter period if local regulations and/or IRBs impose shorter time limits, at a facility selected by Lilly. This retention period enables use of new technologies, response to regulatory questions, and investigation of variable response that may not be observed until later in the development of tirzepatide or after tirzepatide or is commercially available.

## **9.9. Health Economics**

This section is not applicable for this study.

## 10. Statistical Considerations and Data Analysis

### 10.1. Sample Size Determination

Up to 56 subjects are planned to be randomized so that approximately 46 subjects complete the study assuming 15% discontinuation rate. These 56 subjects will be randomized to QW tirzepatide or placebo in a 1:1 ratio. The estimated variability of the change in SMR from baseline is 117 kcal/day (Heilbronn et al. 2006). With an expected treatment difference of 100 kcal/day, this provides at least 80% power for the comparison of tirzepatide versus placebo based on 2 sample t-test using 2-sided test at alpha level of 0.05, and at least 85% power for the sensitivity analysis where only patients who achieve the target weight loss and are considered at least 90% compliant will be included for the assessment of the primary endpoint.

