5.2. Determination of Sample Size

[figure not shown]
Up to 56 subjects are planned to be randomized so that approximately 46 subjects complete the study assuming 15% discontinuation rate. These 56 subjects will be randomized to QW tirzepatide or placebo in a 1:1 ratio. The estimated standard deviation of the change in SMR from baseline is 117 kcal/day (Heilbronn et al. 2006). With an expected treatment difference of 100 kcal/day, this provides at least 80% power for the comparison of tirzepatide versus placebo based on 2 sample t-test using 2-sided test at alpha level of 0.05 for the assessment of the primary endpoint.

Abbreviations: DXA = dual energy X-ray absorptiometry; FCI = Food Craving Inventory; FPQ = Food Preference Questionnaire; QW = once weekly; sMMTT = standardized mixed-meal tolerance test; VAS = visual analog scale.

Figure GPGU.5.1. Illustration of study design for Protocol I8F-MC-GPGU.

Clinical Research Unit Procedures

Abbreviations: DXA = dual energy X-ray absorptiometry; FCI = Food Craving Inventory; FPQ = Food Preference Questionnaire; sMMTT = standardized mixed-meal tolerance test; VAS = visual analog scale.

Figure GPGU.5.2. Illustration of clinical research unit procedures.

6. A Priori Statistical Methods

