6.9.2.1. Primary Pharmacodynamic Analyses Sleep Metabolic Rate

The primary endpoint in the study is the change from baseline (Day -3 to -1) to Week 18 (Day 123 to 125) in sleep metabolic rate (SMR; energy expenditure during sleep period) for comparison of tirzepatide 15 mg versus placebo, which is measured in the respiratory chamber (whole-room calorimetry).

The primary endpoint will be analyzed using analysis of covariance (ANCOVA) to compare the effect of tirzepatide versus placebo at Week 18 on SMR (kcal/day):

- ➤ Independent variables: treatment as a factor, baseline SMR (kcal/day), change from baseline to Week 18 in fat free mass, and change from baseline in fat mass as covariates.
- Response variable: change from baseline to Week 18 in SMR.
- ➤ Where Fat Mass = DXA Region Fat (%)/100 * DXA Weight
- ➤ Where Fat Free Mass = DXA Weight Fat Mass.

Baseline SMR will be analyzed with analysis of variance (ANOVA) with independent variable, treatment as a factor.

Note: Energy expenditure is calculated for sleep period and extrapolated to 24 hours. The calculated sleep metabolic rate (sleep EE in Event Data) will be provided in datasets to statisticians/programmers. The average value of nonmissing measurements at Days -3, Day -2 (two 23-hr sessions) will be used as value for baseline, and the average value of nonmissing measurements at Days 123, Day 124 will be used as value for Week 18.

Inferential statistics include least squares (LS) means and standard error of SMR for tirzepatide versus placebo, the estimated treatment difference (tirzepatide - placebo), and corresponding 2-sided 95% CI, and associated p-value.

Sensitivity analysis on primary endpoint will be conducted in a similar manner on the body weight target population (ie subjects who reach the body weight target range of $-10\% \pm 2\%$ [-8% to -12%, inclusive] at Week 18 from baseline and have evaluable PD data).

Additional analyses will be conducted with ANCOVA with

- Independent variables: treatment as a factor, baseline SMR (kcal/day), change from baseline to Week 18 in DXA weight as covariates
- Response variable: change from baseline to Week 18 in SMR

Additional analyses may be conducted as follows:

- Step 1: conduct ANCOVA model with
 - o Independent variables: baseline fat free mass, baseline fat mass, age, sex
 - o Response variable: baseline SMR
 - Where Fat Mass = DXA Region Fat (%)/100 * DXA Weight
 - Where Fat Free Mass = DXA Weight Fat Mass.

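### The 85% power that protocol 10.1 states for the on-target, 90%-compliant subset does not follow from its stated inputs, which give at most about 81% with 46 completers

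*Protocol*

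**What the plan says.** Protocol 10.1 sets the numbers: "Up to 56 subjects are planned to be randomized so that approximately 46 subjects complete the study assuming 15% discontinuation rate", allocated 1:1. The inputs to the power calculation are each given once: "The estimated variability of the change in SMR from baseline is 117 kcal/day"; "With an expected treatment difference of 100 kcal/day"; and a "2 sample t-test using 2-sided test at alpha level of 0.05". SAP 5.2 makes clear that the 117 is a standard deviation: "The estimated standard deviation of the change in SMR from baseline is 117 kcal/day".

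From these inputs protocol 10.1 claims at least 80% power for tirzepatide against placebo and, in the same sentence, "at least 85% power for the sensitivity analysis where only patients who achieve the target weight loss and are considered at least 90% compliant". It does not say how many subjects are expected in that subset, whether the standard deviation or effect there differs from the overall values, or what the 90% compliance refers to.

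The analysis sections describe the sensitivity analysis differently. The protocol synopsis and protocol 10.3.3.2 restrict it to subjects within 2 percentage points of a 10% weight loss at Week 18. SAP 6.9.2.1 does the same: "subjects who reach the body weight target range of" 8% to 12% loss, with evaluable pharmacodynamic data. None of the three adds a compliance condition. Where treatment compliance is defined, in protocol 7.6 and SAP 6.6.2, the threshold is 75%.

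SAP 5.2 repeats the sample size paragraph but stops after the main comparison: "this provides at least 80% power for the comparison of tirzepatide versus placebo". SAP Section 8 lists this as an update to protocol 10.1 and prints the replacement text. It does not mention the 85% figure or say why it is gone.

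**The concern.** A subset is credited with more power than the full comparison from which it is drawn. At a fixed difference and standard deviation, fewer subjects means less power, so the two figures in the sentence cannot both rest on the inputs printed beside them.

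The on-target analysis is the sensitivity analysis of the primary endpoint. It is run in the weight-matched subjects whom the design sets out to create (protocol 5.4). Anyone working from the protocol would take it to be the better powered of the two analyses and could give a null result there too much weight as evidence against an effect. The stray compliance condition adds a second difficulty: the 85% is attached to a population that no analysis section will analyse.

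**Working it through.** **Inputs.** Difference δ = 100 kcal/day (protocol 10.1); standard deviation σ = 117 kcal/day (protocol 10.1, named as a standard deviation in SAP 5.2); two-sided α = 0.05, two-sample t-test (protocol 10.1); about 46 completers at 1:1, so n = 23 per arm (protocol 10.1).

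**Formula.** Noncentrality λ = δ / (σ√(2/n)), degrees of freedom 2n − 2. Power is the probability that a noncentral t variable with these parameters falls beyond the two-sided critical value.

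**Step 1: reproduce the 80%.** With n = 23, σ√(2/n) = 117 × 0.2949 = 34.50, so λ = 100/34.50 = 2.898 on 44 degrees of freedom. Power is 80.9% (82.6% by the normal approximation). This agrees with the stated figure of at least 80%.

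**Step 2: find the size that gives 85%.** With n = 25, power is 84.2%. With n = 26, σ√(2/n) = 117 × 0.2774 = 32.45 and λ = 3.082; power is 85.6%. So 85% needs 26 per arm, 52 in total. The normal approximation needs 25 per arm, 50 in total, which is still more than 46.

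**Step 3: bound the subset.** Target weight and the endpoint are both assessed at Week 18, and protocol 8.1.1 takes subjects who stop investigational product early out of the study. The subset is therefore no larger than the group with Week 18 data, for which the plan's working figure is about 46. Taking 15% off 56 exactly gives 56 × 0.85 = 47.6; rounding up to 24 per arm gives 82.6% (84.2% by the normal approximation), short of 85% before any restriction is applied. All 56 randomized would give 88.1%, but that leaves no room for the assumed dropout. Reaching 52 would allow only 4 of 56 (7.1%) to be lost to discontinuation, missed target and non-compliance together.

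**Step 4: power as the subset shrinks.** The documents give no subset size, so the totals below are assumptions, split equally between the arms. An unequal split would lower the power further. The last two columns show what would have to change, one at a time, to reach 85%.

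| Subset total | Power at σ 117, δ 100 | σ needed for 85% | δ needed for 85% |
|---|---|---|---|
| 46 | 80.9% | 110.7 | 105.7 |
| 44 | 79.1% | 108.1 | 108.2 |
| 40 | 75.0% | 102.8 | 113.8 |
| 36 | 70.2% | 97.3 | 120.3 |
| 32 | 64.8% | 91.3 | 128.1 |
| 28 | 58.6% | 85.0 | 137.7 |

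**Step 5: try other readings.** A one-sided 0.05 test would reach 85% at about 41 subjects, but the protocol specifies a two-sided test. No reading of the stated inputs that was tried gives 85% in a subset of about 46.

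**The case against.** The strongest reply is that the SAP has already dealt with this. SAP 6.2 requires a protocol amendment only when a principal feature changes; other changes are documented in the SAP. Section 8 names protocol 10.1 and prints replacement text without the 85%. That stands for the analysis itself: nothing planned depends on the figure, and no decision rule rests on the sensitivity analysis. Two things remain. The current protocol still carries the clause. And SAP 6.2 asks for the justification of a change to be documented, whereas Section 8 gives none, so a reader holding both documents cannot tell whether the 85% was withdrawn as unsupported or merely left out.

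A second reply is that power depends on more than numbers. A reader might infer that 85% in the subset is impossible. The documents do not support that. Subjects matched on weight loss could vary less, and a compliant group could show a larger effect; with 40 subjects, a standard deviation of about 103 or a difference of about 114 kcal/day would be enough. But neither document states such a value, so the figure is unsupported rather than impossible. Covariate adjustment in the planned ANCOVA might also reduce the residual variance, but the protocol bases its power on a t-test, and the same model is used for the primary analysis.

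A reader might also conclude that the subset must be smaller than 46, or fix on a particular qualifying fraction. The documents give no subset size; they support only that it can be no larger than the group with Week 18 data.

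Finally, it is tempting to fault the SAP for using a different subset from the protocol. That misplaces the inconsistency. SAP 6.9.2.1 agrees with the synopsis and protocol 10.3.3.2; the odd one out is protocol 10.1.

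**Conclusion.** The point holds as an unsupported power figure in the current protocol. On the only inputs stated, the restricted analysis has at most about 81% power with 46 completers, some 4 points below the claim, and less as the subset shrinks (75.0% at 40, 64.8% at 32, if those were the sizes). These figures assume that the overall standard deviation and difference carry over to the subset, that the arms are equal and that the test is the two-sided t-test named in protocol 10.1. The subset sizes are illustrations, not forecasts.

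The 90% compliance condition conflicts with the protocol's own definition of the sensitivity population and is not used in any analysis section. The consequence is limited to how the sensitivity analysis is read: the planned sample size, the primary analysis and its 80% power stand.

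**What to change.** In protocol 10.1, strike the 85% clause together with its 90% compliance condition. If a statement on the sensitivity analysis is wanted, say that its power is no more than about 81% at the assumed standard deviation and difference with 46 completers, and lower as the subset shrinks. Define the subset as in the synopsis and 10.3.3.2. A higher figure should return only with its own stated subset size, standard deviation and effect.

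In SAP Section 8, add one sentence: the 85% statement in protocol 10.1 is withdrawn because the stated inputs do not support it. The SAP's definition of the sensitivity population needs no change.

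The cost is one deletion and one added sentence. A favourable figure is lost; the design, sample size and analyses stay as they are.
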